	6.1.9 Duration of Therapy				
	6.1.10 Tracking of Dose				
7	7 STUDY PROCEDURES AND SCHEDULE				 16
	7.1 STUDY SPECIFIC PROCEDURES				16

Study number: s18-01530 Version: 11 Jan 2021 Page v

Version: 11 Jan 2021

List of Abbreviations

AE Adverse Event/Adverse Experience

CFR Code of Federal Regulations

CRF Case Report Form

CSOC Clinical Study Oversight Committee

DCC Data Coordinating Center

DHHS Department of Health and Human Services

DSMB Data and Safety Monitoring Board

FFR Federal Financial Report
FWA Federalwide Assurance
GCP Good Clinical Practice

HIPAA Health Insurance Portability and Accountability Act

ICF Informed Consent Form

ICH International Conference on Harmonisation

IRB Institutional Review Board
ISM Independent Safety Monitor

MOP Manual of Procedures

N Number (typically refers to participants)

NIH National Institutes of Health

OHRP Office for Human Research Protections
OHSR Office of Human Subjects Research

PI Principal Investigator

QA Quality Assurance

QC Quality Control

SAE Serious Adverse Event/Serious Adverse Experience

SOP Standard Operating Procedure

US United States

Version: 09 Sep 2020

Protocol Summary

Title	Fenfluramine in CKDL5 Deficiency Disorder (CDD)		
Brief Summary	We will enroll 10 patients, ages 2-35 years old, with a confirmed genetic/clinical diagnosis of CDKL5 Deficiency Disorder (CDD) in an open label trial of fenfluramine for seizure control. Protocol – patients will be titrated over 14 days to a dose of ZX008 0.8 mg/kg/day (maximum dose 30 mg/d)		
Phase	NA		
Objectives	Decrease in seizure frequency and change in impression and quality of life		
Methodology	Open label		
Endpoint	Primary outcome: Median monthly convulsive seizure frequency Secondary outcomes: 1. Caregiver/Investigator Global Impression of Change (C/IGIC). The parent/caregiver and investigator rated change on a 7-point scale: 1-very much improved; 2-much improved; 3-minimally improved; 4-no change; 5-minimally worse; 6-much worse; and 7-very much worse 2. Quality of Life in Childhood Epilepsy Scale (13). A low-burden parent/caregiver completed assessment that looks at how epilepsy affects day-to-day functioning of their child in various life areas, including physical activities, well-being, cognition, social activities, behavior and general health. 3. Pediatric Quality Of Life Inventory (PEDS-QL). A parent/caregiver completed assessment that looks at how epilepsy affects day-to-day functioning of their child in various life areas, including physical activities, well-being, cognition, social activities, behavior and general health during a specific time frame		
Study Duration	14 weeks with extension available		
Duration of IP administration	14 weeks with extension available		
Population	confirmed genetic/clinical diagnosis of CDKL5 Deficiency Disorder (CDD)		
Study Sites	1: NYU Comprehensive Epilepsy Center.		
Number of participants	10 patients: 7: ages 2-18 years old Max of 3: ages 18-35 years old		
Description of Study Agent	Liquid		
Key Procedures	Blood draws, questionnaires, Doppler echocardiogram, electrocardiogram		

Page 2 Study number: s18-01530

Version: 11 Jan 20									
Protocol Activity: Week (±7 days)	Baseline Week 0	Safety call	Week 2	Week 6	Safety call	Week 10	Safety call	Week 14	Post Taper Follow up
Visit	1	Safety call	2	3	Safety call	4	Safety call	5/End of study/ End of treatment/ Withdrawal visit	
Informed consent/assent	X								
Inclusion/exclusion criteria	X	X	X	X	X	X	X	X	
Medical history	X	X	X	X	X	X	X	X	X
Demographics	X		I	I.	I .	I	1	T	
Physical and neurological exam and Vital signs	X		X	X		X		X	
Adverse events	X	X	X	X	X	X	X	X	X
EKG	X			X				X	
Echo	X		37	X		37		X	
C/IGIC	X		X	X		X		X	
QOLCE PEDS-QOL	X		X	X		X		X	
Hematology & Chemistry (draw/handling) (CBC, CMP, LFTs, BUN, Creatinine), Coagulation	X		X	X		X		X	
HCG (urine and serum)	X		X	X		X		X	
THC (urine and serum)	X		X	X		X		X	
Urinalysis	X		X	X		X		X	
AED levels /Clobazam	X			X		X		X	
Study diary provided	X		X	X		X		X	
Study diary collected			X	X		X		X	
Study drug dispensed	X		X	X		X		X*	
Study Drug administration	X								
Study drug compliance dosing schedule and return dosing schedule	X	X	X	X	X	X	X	X	X
Concomitant/other medications/supplements	X	X	X	X	X	X	X	X	X

Version: 11 Jan 2021

				Exte	ension			
Protocol Activity: Week (±7 days)	Exten sion Visit	Safety call	Extension Visit	Safety call	Extension Visit	Safety call	End of Treatment/ Withdrawal	Post Taper Follow up
Inclusion/excl usion criteria	X	X	X	X	X	X	X	
Medical history	X	X	X	X	X	X	X	X
Physical and neurological exam and Vital signs	X		X		X		X	
Adverse events	X	X	X	X	X	X	X	X
EKG	X		X		X		X	
Echo	X		X		X		X	
C/IGIC	X		X		X		X	
QOLCE	X		X		X		X	
PEDS-QOL	X		X		X		X	
Hematology & Chemistry (draw/handlin g) (CBC, CMP, LFTs, BUN, Creatinine), Coagulation	X		X		X		X	
HCG (urine and serum)	X		X		X		X	
THC (urine and serum)	X		X		X		X	
Urinalysis	X		X		X		X	
AED levels /Clobazam	X		X		X		X	
Study diary provided	X		X		X		X	
Study diary collected	X		X		X		X	
Study dispensed	X		X		X		X	
Study drug compliance dosing schedule and return dosing schedule	X	X	X	X	X	X	X	X
Concomitant/ other medications/s upplements	X	X	X	X	X	X	X	X

^{*}If subject continues to extension visit

Version: 11 Jan 2021

1. Key Roles

Principal Investigator: [name]

New York University Comprehensive Epilepsy Center

[name] US [contact]

Email: [contact]

2. Introduction, Background Information and Scientific Rationale

2.1Background Information and Relevant Literature: Name and Description of the Investigational Agent

Fenfluramine is an amphetamine analogue that was synthesized many years ago. It was approved in a large number of countries and widely prescribed as an appetite suppressant for the treatment of adult obesity. Brand names for fenfluramine formulations included Ponderax and Pondimin. Fenfluramine was also used extensively in an off-label combination with phentermine ("Fen-Phen") to treat adult obesity. Fenfluramine is a racemic compound and the single enantiomer D-fenfluramine (dexfenfluramine) was also approved and marketed for the treatment of obesity as Adifax, Redux, and others.

Fenfluramine was introduced in the USA in 1973. Products containing fenfluramine and D-fenfluramine were withdrawn from all markets between 1997 and 2000 after reports of heart valve disease and pulmonary hypertension (Connolly 1997; CDC 1997; Wong 1998). While the risk/benefit relationship for fenfluramine was considered unfavorable to treat obesity in adults, establishing seizure control in Dravet syndrome, Lennox-Gastaut syndrome (LGS) or other refractory catastrophic childhood epilepsies might lead to a more acceptable risk/benefit profile for fenfluramine. The high rate of mortality and severe intellectual and quality of life impairments in severe childhood epilepsies^{1, 2} makes any effective drug or therapy a potentially life-saving option.

As a result of the earlier extensive use of fenfluramine in adult obesity, there is a large body of information in the public domain concerning its pharmacology, toxicology and use in the treatment of obesity. These data are summarized in the ZX008 Investigator Brochure (2017).⁴ There is also a large body of information concerning its clinical safety profile.

2.1.1 Preclinical Data

The pharmacokinetics of fenfluramine, norfenfluramine and their respective isomers have been studied in mice, rats, dogs and humans. Fenfluramine and norfenfluramine were more slowly eliminated in humans than in other species. In vitro metabolism studies have shown considerable species differences in the metabolism of fenfluramine, with no single species having a profile similar to humans. No human-specific metabolites were detected and both rat and dog showed good coverage of the human fenfluramine metabolites. In humans, fenfluramine is metabolized primarily to norfenfluramine. Fenfluramine is partially metabolized by CYP1A2, CYP2B6, and CYP2D6, with additional metabolism by CYP2C9, CYP2C19, and CYP3A4. Norfenfluramine does not appear to be strong substrate of any CYP450 enzyme, but is metabolized by CYP1A2, CYP2B6, CYP2C19, and CYP2D6 in vitro. There is also some contribution of renal clearance to the elimination of dexfenfluramine (8%-16%) and nordexfenflurmaine (7%-8%) from the body. Because fenfluramine and its active metabolite

Version: 11 Jan 2021

norfenfluramine have multiple pathways of elimination, interference with a single pathway is unlikely to cause a significant change in fenfluramine's clearance though the probability of an interaction increases if multiple elimination mechanisms are affected simultaneously.

While in vitro studies showed that both fenfluramine and norfenfluramine cause weak inhibition of CYP2D6 and fenfluramine causes weak induction of CYP3A4 and CYP2B6, further analysis based on the FDA's mechanistic static model shows that fenfluramine and its major metabolite norfenfluramine are unlikely to alter the pharmacokinetics of substrates of CYP450 enzymes in the range of ZX008 doses that will be administered in this study. A 10-week GLP juvenile toxicology and toxicokinetic study in rats, which included fenfluramine doses of 3.5, 9 and 20 mg/kg/day by oral gavage for 10 weeks (Days 7 to 76 pp). The data from the juvenile toxicology studies suggest that the effects of fenfluramine in juvenile animals (CNS-related clinical signs, effects on body weight and food consumption, and neurobehavioral deficits) are similar to effects previously reported in neonatal and adult rats (Morford, 2002; Williams, 2002). There was no evidence of CNS histopathology; importantly, there were also no histopathologic findings in aortic or mitral cardiac valves, and no adverse effects on any other tissues at necropsy.

The lowest-observed-adverse-effect level (LOAEL) of 3.5 mg/kg/day is a human equivalent dose (HED) of 0.833 mg/kg/day when converted on the basis of body surface in mg/m2, based on a reference body weight for a 20-kg child. No new target organs were identified in juvenile animals, and there were no permanent effects on sexual maturation or reproductive function when juvenile animals were administered fenfluramine from the neonatal period through adulthood.⁴

2.1.2 Clinical Data in Epilepsy

There have been several published reports of fenfluramine's successful treatment of refractory childhood epilepsy in the 1980s. (Aicardi and Gaustaut, 1985; Aicardi et al., 1988). In 1996, a Belgian group reported on the use of fenfluramine in 11 children (ages 18 months to 15.5 years old) with refractory or self-induced epilepsy (Boel and Casaer, 1996). Patients were treated with fenfluramine at 0.5 - 1 mg/kg/day for 3 to 8.5 years (average duration 5 years 7 months). Seven children (64%) became seizure-free and the remaining 4 patients experienced \geq 75% reduction in seizure frequency.

In 2002, Casaer and Boel published an update of their fenfluramine study. The study population was expanded to 22 patients with intractable or self-induced seizures, including the previous 11 patients (Casaer and Boel, 2002). The duration of treatment was 1 to 12 years. Among the 22 patients treated, 6 (27%) became seizure-free, 10 (45%) had a 90% reduction in seizure frequency and 6 (27%) were non-responders. Fenfluramine was effective in multiple seizures types in Dravet syndrome (DS), a drug resistant pediatric epileptic encephalopathy syndrome (Ceulemans et al., 2012; Schoonjans 2015 et al.; Ceulemans et al., 2016). 4

Zogenix is currently evaluating ZX008 in DS in three Phase 3 double-blind, randomized, placebo-controlled studies (clinicaltrials.gov identifiers: NCT02826863, NCT02682927, and NCT02926898). Currently, a cohort of refractory Lennox-Gastaut syndrome (LGS) patients in Belgium are being treated in a Phase 2 open-label, pilot, dose-finding trial of fenfluramine as an add-on therapy to conventional therapy (Study S58545; clinicaltrials.gov identifier: NCT02655198). Subjects aged 3 to 18 years, fulfilling the diagnostic criteria for LGS as described by the International League Against Epilepsy (ILAE) in 1989, who have failed at least two AEDs (including vagal nerve stimulation (VNS), and have had at least 4 documented convulsive seizures (generalized tonic-clonic, tonic, atonic, and focal seizures with a motor

Version: 11 Jan 2021

component and on at least 2 AEDs at stable doses in the prior 4 weeks are eligible for this study (Lagae et al., 2016). A similar study has been initiated in the United States.⁴

For the Belgium LGS study, subjects establish baseline convulsive seizure frequency over 4 weeks and are then treated with fenfluramine at a starting dose of 0.2 mg/kg/day. In non-responders (<50% convulsive seizure frequency decrease), the dose is up titrated every 4 weeks from 0.2 mg/kg/day to 0.4 mg/kg/day, and up to a maximum dose of 0.8 mg/kg/day for up to 20 weeks if the patient remains a non-responder per protocol definition.⁴

Interim results are available on the anticonvulsant effects of adjunctive treatment with ZX008 in the first 13 patients with LGS from Study S58545 (9 males, 4 female). Fenfluramine treatment was started at a mean age of 11.4 years (range 3 to 17 years), administered at a maximum of 0.8 mg/kg/day and added to each patient's current AED regimen. Prior to enrolling in the trial, all patients had failed on at least 3 other AEDs. By November 2016, 8 patients had completed all 20 weeks of the treatment period, 4 patients withdrew before study end, and 1 patient remained on treatment, having completed 16 weeks of treatment. Of the 4 patients who withdrew before study end, 1 withdrew due to worsening of seizures following elective surgery, and 3 withdrew due to adverse events (2 decreased alertness, 1 insomnia). Seven of the 13 patients (54%) achieved at least a 50% reduction in the number of convulsive seizures during the study at doses of 0.2mg/kg (3 patients), 0.4mg/kg (3 patients) and 0.6mg/kg (1 patient). Despite not attempting to dose to maximal efficacy a dose response appears to be emerging with a 2-fold increase in the number of responders at the 0.4 mg/kg/day vs. 0.2 mg/kg/day dose. The most common treatment emergent adverse events to date include decreased appetite in 3 patients, decreased alertness/fatigue in 3 patients, and insomnia in 2 patients. ZX008 has been well tolerated in this small, open-label study, and no patients have exhibited any clinical signs of cardiovascular or cardiopulmonary adverse events as of the November 2016 data cut. (ZX008 IB 2017).⁴

2.1.3 Dose Rationale

Based on clinical data to date. Patient will be dosed up to 0.8 mg/kg/d or 30 mg/d maximum. It will be twice daily dosing. Fenfluramine was administered to over 500 children with neurobehavioral conditions, including autism and ADHD with good safety and tolerability, at doses in the range of 0.65 to 3.6 mg/kg/day (most common dose of 1.5 mg/kg/day) for up to 12 months.⁴

2.2 Rationale

The lack of consistent efficacy and individual tolerability and safety concerns with current treatments available have resulted in the continued significant unmet need for a new treatment with a novel mechanism of action for children and adults with CDD.

2.3 Potential Risks & Benefits

Fenfluramine is effective in multiple seizures types in Dravet syndrome (DS), another very drug resistant pediatric epileptic encephalopathy syndrome. In a recent Phase III study of 119 DS patients, the median reduction of convulsive seizures was 64% greater than placebo³ in the group that received 0.8 mg/kg/day and 34% for the group that received 0.2 mg/kg/day of fenfluramine.

2.3.1Side effects

The most common AEs observed in children and young adults the ongoing studies of

Version: 11 Jan 2021

ZX008 include decreased appetite, pyrexia, diarrhea, lethargy, and somnolence. However, there is limited data in the pediatric population, largely based on the Belgium and the more recent Phase 3 trial cited above.⁴

2.3.2 Echocardiogram findings

Findings from echocardiograms will be discussed between the investigator, local cardiologist and parent/caregiver/legal or authorized representative to determine risk versus benefit of the study to the subject.

ECHOs will be done at NYU. If caregivers/patients are not able to travel to NYU facility, doppler echocardiography can be done at a local facility. Readings will be sent back to site for evaluation. Findings related to pulmonary hypertension or valvulopathy on any of the four valves (aortic, mitral, pulmonary, tricuspid) will be reported to the investigator with grades of normal, trace, mild, moderate or severe. If the ECHO result has progressed in severity since the last reading, then new oversight measures will be enacted as described below in Levels 1-3. Table 12 describes the severity of ECHO findings with the level of increasing oversight if the subject is to remain in the study.

Table 1: Clinical Measures Enacted Upon Increasing Severity of ECHO Findings

	Valve					
Severity	Aortic	Mitral	Pulmonary	Tricuspid		
Normal	Level 1	Level 1	Level 1	Level 1		
Trace	Level 2	Level 2	Level 1	Level 1		
Mild	Level 2	Level 2	Level 1	Level 1		
Moderate	Level 3	Level 3	Level 3	Level 3		
Severe	Level 3	Level 3	Level 3	Level 3		

Level 1: Continue per protocol

Level 2:

- 1. If there is a desire to continue study medication:
 - a. The investigator will evaluate the efficacy to date based on study diaries and consult with the parent/guardian, and determine whether study treatment was associated with significant, meaningful benefit in number, severity and/or duration of seizures and/or on the impact on daily functioning.
 - b. The investigator will consider whether the subject has had reasonable trials (dose and duration) of other available anticonvulsants (e.g. valproic acid, clobazam, or topiramate), alone or in combination, and not maintained the level of seizure control achieved with study medication.
- 2. If the investigator feels consideration of continued treatment is warranted considering benefit and potential risk, and the parent/guardian feels strongly that the child be maintained on the study medication when understanding the risks, the parent/guardian must sign a new consent which describes the additional risk and the child should provide assent if appropriate.
 - a. If both of these conditions are not met, the subject is discontinued from treatment.

Study number: s18-01530 Page 8
Version: 11 Jan 2021

3. Investigator and Institutional Cardiologist make a determination of appropriate path, including the possible outcomes:

- a. Discontinue study medication
- b. Increase frequency of ECHO and ECG monitoring
- c. Add additional ECG and/or ECHO measures to be monitored
- d. Reduce the dose of study medication

Level 3:

- 1. The investigator will evaluate efficacy to date based on study diaries and consult with the parent/guardian, and determine whether the achieved benefit justifies the consideration of continuing study treatment. MINIMAL efficacy criteria:
 - a. Seizures must be more than 75% improved (number of convulsive seizures per 28 days) on treatment over baseline, and improvement must be consistent.
 - b. The number, type, duration, and distribution of seizures at baseline should be of a severity, which justifies the risks of cardiopulmonary complications, considering the subject's age and overall health.
 - c. Subject has had reasonable trials (dose and duration) of other available anticonvulsants (e.g., valproic acid, clobazam, topiramate), alone or in combination, and not maintained the level of seizure control achieved with study medication.
- 2. If the investigator feels consideration of continued treatment is warranted considering benefit and potential risks, and the parent/guardian feels strongly that the child be maintained on the study medication when understanding the risks, the parent/guardian must sign a new consent, which describes the additional risks and the child should provide assent if possible.
 - a. If both of these conditions are not met, the subject is discontinued from treatment.
- 3. Investigator and Institutional Cardiologist make a determination of appropriate path, including these possible outcomes:
 - a. Discontinue study medication
 - b. Increase frequency of ECHO and ECG monitoring
 - c. Add additional ECG and/or ECHO measures to be monitored
 - d. Reduce the dose of study medication

3. Objectives and Purpose

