5.6 Participant Withdrawal or Termination

5.6.1 Reasons for Withdrawal or Termination

A subject may be discontinued from study drug at any time if the subject, subject's legal guardian, or the investigator feels that it is not in the subject's best interest to continue. The following is a list of possible reasons for study drug discontinuation:

- 1. Parental/legal guardian withdrawal of consent.
- 2. Subject is not compliant with study procedures.

Study number: s18-01530 Page 13 Version: 11 Jan 2021

3. Protocol violation requiring discontinuation of study drug.

- 4. Severe adverse events, including significant toxicity such as severe cognitive or behavioral toxicity, impaired liver and renal function, or impaired hematopoiesis
- 5. Seizure exacerbation not attributable to other known provocative factors.
- 6. Interaction with concomitant AED regimen that leads to unacceptable toxicity. Medication adjustments will be avoided, if possible, and may require the subject to exit the study, at the discretion of the Investigator.

Specific drug-related toxicities will be assessed and managed by the Principal Investigator.

Depending on the nature of the signs (eg, changes in serum chemistries, liver function tests) or symptoms (eg, rash), the subject will be assessed to determine the severity and likelihood of relation to study medication. Based on this assessment, the medication may be discontinued, the dose may be reduced, or the drug may be continued with ongoing assessment. If the study drug is discontinued due to a suspected toxicity, it will only be restarted if there is strong evidence that the toxicity was likely not related to the study medication (eg, liver tests were elevated due to a cytomegalovirus infection).

If a subject must discontinue study drug, the method for discontinuation from study drug will be determined based on the type of reaction and/or reason for withdrawal. For example, if the subject experiences a rapidly progressive rash, it would lead to abrupt cessation of study drug, but if subject experiences excess tiredness, study drug may be tapered off. A discussion of the method of cessation will occur between the subject and/or subject's parent/legal guardian and the physician.

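### Pulmonary hypertension is graded on ECHO but has no Level in Table 1, so it does not clearly trigger the re-consent step or the Level 3 benefit benchmark

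*Combined protocol and SAP*

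**What the plan says.** Section 2.3.2 covers two kinds of ECHO finding: "Findings related to pulmonary hypertension or valvulopathy on any of the four valves (aortic, mitral, pulmonary, tricuspid) will be reported to the investigator". Both are reported on one scale of five grades, from normal to severe. The section continues: "If the ECHO result has progressed in severity since the last reading, then new oversight measures will be enacted as described below in Levels 1-3". That trigger is the ECHO result as a whole and is not limited to valves.

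Table 1 turns grade into Level. Its columns stand under the header Valve and are aortic, mitral, pulmonary and tricuspid.

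The Levels carry these consequences:
- Level 1: carry on as planned.
- Level 2: for treatment to continue, "the parent/guardian must sign a new consent which describes the additional risk", and the investigator must judge continuation warranted. Otherwise: "If both of these conditions are not met, the subject is discontinued from treatment".
- Level 3: a matching consent step and stop clause, plus minimal efficacy criteria. The numeric one reads: "Seizures must be more than 75% improved (number of convulsive seizures per 28 days) on treatment over baseline, and improvement must be consistent". Another asks whether baseline seizure severity "justifies the risks of cardiopulmonary complications".

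Elsewhere, section 7.3 has readings returned for valve disease and pulmonary hypertension and refers to ECHO abnormality thresholds set by the sponsor. Section 8.1 names only valve regurgitation as graded.

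**The concern.** Section 2.1 gives two reasons for the drug's withdrawal from the market: heart valve disease and pulmonary hypertension. Section 2.3.2 has both graded and makes progression of the ECHO result the trigger for action, but the table that assigns the action covers only the valves.

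At stake are two specific safeguards. One is a new signed consent describing the added risk, which matters because most participants are children and a parent decides for them. The other is the Level 3 benchmark, which is much stricter than the 40% reduction needed to enter the extension. Without an assigned Level, whether either applies to pulmonary hypertension depends on how the reader fills the gap. The extension has no fixed end, so exposure could be long.

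**Working it through.** The plan has no figure to reproduce here. The check compares what section 2.3.2 grades with what Table 1 maps.

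**Step 1. Count Table 1.** 5 grades × 4 valves = 20 cells, all filled.

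| Grade | Aortic, mitral | Pulmonary, tricuspid |
|---|---|---|
| Normal | Level 1 (2 cells) | Level 1 (2 cells) |
| Trace | Level 2 (2) | Level 1 (2) |
| Mild | Level 2 (2) | Level 1 (2) |
| Moderate | Level 3 (2) | Level 3 (2) |
| Severe | Level 3 (2) | Level 3 (2) |

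Level 1: 4 + 4 = 8. Level 2: 4. Level 3: 4 + 4 = 8. Total 8 + 4 + 8 = 20. Pulmonary hypertension grades with a Level: 0 of 5.

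**Step 2. Could the Pulmonary column mean pulmonary hypertension?** No. It stands under Valve, and the text lists pulmonary as one of the four valves. Each row holds exactly four Levels for four named valves, so nothing suggests a column lost in reading the file.

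**Step 3. Can the Level be inferred from grade alone?**
- Moderate and severe: all 8 cells are Level 3, and the Level 3 text speaks of cardiopulmonary risk. Level 3 is a fair inference, but it is not stated.
- Trace and mild: 4 cells are Level 2 and 4 are Level 1. No inference works.

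**Step 4. Does another section supply a Level?** Section 7.3 looks for pulmonary hypertension but attaches no action to it. Section 8.1 grades valve regurgitation only. Sections 5.6.1 (discontinuation), 8.1.1 (adverse event definition) and 8.7 (halting) assign no Level. The sponsor's thresholds in 7.3 are not reproduced and are not tied to Levels.

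**Step 5. Which patients fall in the gap?** Those whose pulmonary hypertension grade has progressed without a valve progression that itself brings Level 2 or 3 (aortic or mitral at trace or worse, pulmonary or tricuspid at moderate or worse).

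**Step 6. A worked case.** Take, for illustration, a 50% reduction in convulsive seizures. 50% ≥ 40%, so the response threshold for the extension is met (sections 4.2.1, 7.5.1 and 7.5.2). 50% is not more than 75%, so the Level 3 minimal criterion fails. After progression to moderate on any valve, the Level 3 criterion and re-consent apply. With moderate pulmonary hypertension and no qualifying valve grade, the document does not say that they do. The two tests disagree for any reduction from 40% up to and including 75%.

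**Step 7. How often must the rule be applied?** On-treatment core ECHOs at weeks 6 and 14 in 10 patients: 2 × 10 = up to 20 readings. In the extension, every 3 months gives 12 / 3 = 4 per patient-year (52 / 12 = 4.3 on the 12-week schedule of 7.5.2). These count scheduled readings, not events.

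**The case against.** The strongest reply is that pulmonary hypertension is not left unmanaged. Section 2.3.2 opens with a duty that is not limited to valves: "Findings from echocardiograms will be discussed between the investigator, local cardiologist" and the family, to weigh risk against benefit. An abnormal result counts as an adverse event under 8.1.1 if it is clinically significant or leads to further tests or treatment. Section 5.6.1 adds: "A subject may be discontinued from study drug at any time". Section 8.7 provides for ad hoc review with the company. All of this stands, and it lessens the consequence. None of it requires new written consent or applies the 75% benchmark.

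A reader might infer that the protocol fixes when the drug must stop for valve disease and has no such rule for pulmonary hypertension. The documents do not support that contrast. The stop clause at Levels 2 and 3 depends on the investigator's view that continuation is warranted and on the parent's strong wish and signed consent. The investigator and cardiologist then choose among stopping, closer monitoring and a lower dose. Handling of valve findings can therefore also vary between patients. A reader might also infer that a patient with pulmonary hypertension is meant to carry on. No passage says so.

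Two further objections hold in part. Level 3 can reasonably be read across to moderate and severe, so the part with no workable inference is trace and mild. And with about 10 patients at one site under one principal investigator, variation between readers is limited, although 2.3.2 and 7.3 allow ECHOs at local facilities.

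**Conclusion.** The point holds as a gap in a safety-management rule. Section 2.3.2 grades pulmonary hypertension and says progression brings in Levels, but 0 of its 5 grades has one, against 20 of 20 valve cells. Without a qualifying valve grade, the written re-consent of Levels 2 and 3 and the Level 3 benchmark are not clearly triggered. The claim goes no further than that.

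It rests on two assumptions. First, Table 1 is the whole map; the text cites a Table 12, but what it describes there is what Table 1 contains. Second, the sponsor's thresholds, which are not in the document, do not themselves assign Levels; 2.3.2 says that the Levels apply as set out in that section. No rate of pulmonary hypertension is given, so the number of patients affected is unknown. No endpoint or analysis changes. The change is a cheap improvement.

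**What to change.** - Add a pulmonary hypertension column to Table 1. Put moderate and severe at Level 3, as in all 8 existing cells for those grades, and normal at Level 1.
- Put trace and mild at Level 2 as the cautious default, as for the aortic and mitral valves, unless the investigator and cardiologist fix Level 1 in advance, as for the pulmonary and tricuspid valves.
- State how pulmonary hypertension is graded. Use the sponsor's thresholds cited in 7.3 if they cover it, and otherwise a definition agreed with the cardiologist. Without this, the new column would attach Levels to undefined grades.
- Extend section 8.1 so that both valve regurgitation and pulmonary hypertension are graded.

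The cost is a small amendment and the work of settling the grading definition. No scheduled procedure is added, since the ECHO is already done and pulmonary hypertension is already reported. The downside is that a false-positive reading could lead to re-consent or stopping in a patient with few other options. A repeat ECHO before acting would limit that.
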